Appendix 3 Shells of Tables, Figures, Listings

The TFL shells for this study are provided in a separate document titled "Gan & Lee GL-GLAT1-3001 TFL Shells Version 3.0_updated_annotated.docm," which includes a complete table of contents listing all required outputs.

Type of Deviation/ Code	Deviation Description	Important protocol deviation	Sub-Category	PD Effect on Immunogenicity	PD Effect on Efficacy
2. EXCLUSION CRITERIA n. 3	Enrollment of subject with diabetic ketoacidosis within a year before screening.	Yes	3	No	No
2. EXCLUSION CRITERIA n. 4	Enrollment of a subject with a history of brittle type 1 diabetes mellitus within the year before screening (e.g., multiple hospitalizations related to diabetes mellitus and/or severe hypoglycemia for which the subject required 3rd party assistance).	Yes	4	Yes	Yes
2. EXCLUSION CRITERIA n. 5	Enrollment of a subject with any severe, delayed sequelae of diabetes mellitus, e.g., worsening end-stage renal disease, advanced coronary artery disease, or myocardial infarction within the year before screening, or autonomic peristaltic problems, e.g., gastroparesis.	Yes	5	Yes	Yes
2. EXCLUSION CRITERIA n. 6	Enrollment of a subject with anticipated change in insulin used during the study.	Yes	6	Yes	Yes
2. EXCLUSION CRITERIA n. 7	Enrollment of a subject without obtaining TSH and T4 results before randomization and both TSH and T4 results are within normal ranges measured by the central laboratory after randomization (during the treatment period).	Yes	7.1	No	No
2. EXCLUSION CRITERIA n. 7	Enrollment of a subject without obtaining TSH and T4 results before randomization and TSH and/or T4 results are not available or out of normal ranges after randomization (during the treatment period).	Yes	7.2	Yes	Yes
2. EXCLUSION CRITERIA n. 8	Enrollment of a subject with $BMI < 19 \text{ kg/m}^2$ or $> 35 \text{ kg/m}^2$.	Yes	8	Yes	Yes
2. EXCLUSION CRITERIA n. 9	Enrollment of a subject without obtaining hematology or chemistry tests or any clinically significant (in the opinion of the investigator) hematology or chemistry test results at screening, including any liver function test $> 3 \times$ the upper limit of normal.	Yes	9	Yes	Yes
2. EXCLUSION CRITERIA n. 10	Enrollment of a subject with documented anti-insulin antibodies in the past.	Yes	10	Yes	Yes
2. EXCLUSION CRITERIA n. 11	Enrollment of a subject treated with glucocorticosteroids (newly prescribed or high dose), immunosuppressants, or cytostatic agents within 60 days before screening; or treated with a prohibited medication up to randomization.	Yes	11	Yes	Yes

Gan & Lee Pharmaceuticals USA

Sponsor: Gan & Lee Pharmaceuticals USA Corporation
Protocol no.: GL-GLAT1-3001

Statistical Analysis Plan
Version Date: 27-May-2021

Type of Deviation/ Code	Deviation Description	Important protocol deviation	Sub-Category	PD Effect on Immunogenicity	PD Effect on Efficacy
	follow-up procedures; or any other factor that would indicate a significant risk of loss to follow up.				
2. EXCLUSION CRITERIA n. 23	Enrollment of a subject with intolerance or history of hypersensitivity to insulin glargine or any excipient of IP.	Yes	23	Yes	Yes
2. EXCLUSION CRITERIA n. 24	Enrollment of a subject unable or unwilling to wear the CGM sensor as required for the study, or to comply with the concomitant medication requirements in the FreeStyle Libre Pro Indications and Important Safety Information, during the CGM periods.	Yes	24	No	No
3. STUDY DRUG / INVESTIGATIONAL PRODUCT (IP)	Deviations related to study drug				
3. STUDY DRUG	A single dose of study drug is not administered by the subject due to reason(s) other than safety in any given 2-week span during treatment period.	No	1	No	No
3. STUDY DRUG	More than one dose of study drug is not administered by the subject due to reason(s) other than safety in any given 2-week span during treatment period.	Yes	2	No	Yes
3. STUDY DRUG	Subject received the study drug that was assigned to another subject, which is consistent with their assigned treatment.	No	3	No	No
3. STUDY DRUG	Subject received the study drug that was assigned to another subject, which is different than their assigned treatment.	Yes	4	Yes	Yes
3. STUDY DRUG	Subject failed to return the study drug.	No	5	No	No
3. STUDY DRUG	Failure to adjust doses of the study drug according to the instructions provided by the Investigator (especially where doses are expected to have a major impact on outcome) during the treatment period or failure to adjust the previously prescribed basal insulin during the Dose Optimization period.	Yes	6	No	Yes
3. STUDY DRUG	BID dosing of the study drug.	No	7	No	No
3. STUDY DRUG	GCP compliance - Drug Accountability not properly documented by site staff.	No	8	No	No
3. STUDY DRUG	A temperature excursion occurred and the proper notification, quarantine and release	No	9	No	No

Sponsor: Gan & Lee Pharmaceuticals USA Corporation
Protocol no: GL-GLAT1-3001

PRA HEALTH SCIENCES

Statistical Analysis Plan
Version Date: 27-May-2021

Type of Deviation/ Code	Deviation Description	Important protocol deviation	Sub-Category	PD Effect on Immunogenicity	PD Effect on Efficacy
4. ASSESSMENT - SAFETY	Failure to complete single or multiple safety assessments (hematology, chemistry, thyroid labs, urinalysis, pregnancy test, vital signs, body weight, ECG, PE) at the final or Early Termination (ET) visit.	Yes	7	No	No
4. ASSESSMENT - SAFETY	AEs not assessed at a study visit (excluding hypoglycemia and not clinically significant hyperglycemia).	Yes	8	No	No
4. ASSESSMENT - SAFETY	Subject becomes pregnant during the study and is not withdrawn from the study.	Yes	9	No	No
4. ASSESSMENT - SAFETY	Partner of a male subject becomes pregnant during the study and pregnancy not reported.	Yes	10	No	No
4. ASSESSMENT - SAFETY	Failure to repeat laboratory tests for unexplained abnormal laboratory test results.	No	11	No	No
4. ASSESSMENT - SAFETY	A failure to complete multiple safety assessments (hematology, chemistry, thyroid labs, urinalysis, pregnancy test, vital signs, body weight) at a single visit.	Yes	12	No	No
4. ASSESSMENT - SAFETY	Failure to complete urine pregnancy test for all women of childbearing potential at study visit(s) and confirmed pregnancy later.	Yes	13	No	No
4. ASSESSMENT - SAFETY	Failure to follow the protocol (or any safety related plans) such that the safety of the subject or other subjects in the study is significantly impacted.	Yes	14	No	No
5. ASSESSMENT - EFFICACY	Failure to complete any efficacy assessments at study visits.				
5. ASSESSMENT - EFFICACY	Failure to complete HbA1c and/or Fasting Blood Glucose sampling at two consecutive visits, or at Baseline (Screening or Day 1), or at V9/Early Termination.	Yes	1	No	Yes
5. ASSESSMENT - EFFICACY	Failure to complete HbA1c and/or Fasting Blood Glucose sampling at a visit other than at Baseline (Screening or Day 1), or at V9/Early Termination.	No	2	No	No
6. VISIT WINDOW	Whole visit missed on or out of visit window.				
6. VISIT WINDOW	Missing an entire visit	No	1	No	No
6. VISIT WINDOW	Visit or procedure out of window	No	2	No	No
7. INFORMED CONSENT (ICF)	ICF process not conducted per ICH/GCP Guidelines or CFR.				

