#### **STUDY POPULATION AND MAIN CRITERIA FOR INCLUSION/EXCLUSION:**

Subjects cannot be enrolled or randomized until all inclusion criteria (including test results) are confirmed.

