**Exclusion Criteria:**

1. Participation in another clinical study or use of any study drug within 30 days before screening
2. Previous use of a biosimilar insulin, either basal or bolus
3. Diabetic ketoacidosis within a year before screening
4. Brittle type 1 diabetes mellitus within the year before screening (e.g., multiple hospitalizations related to diabetes mellitus and/or severe hypoglycemia for which the subject required 3rd party assistance)
5. Any severe, delayed sequela of diabetes mellitus, e.g., worsening end-stage renal disease, advanced coronary artery disease, or myocardial infarction within the year before screening, or autonomic peristaltic problems, e.g., gastroparesis
6. Anticipated change in insulin used during the study (change in dosage is allowed, but change in type or brand of insulin will result in the subject being withdrawn from the study)
7. Inadequately controlled thyroid disease, defined as a TSH or free T4 value > the upper limit of normal
8. BMI < 19 kg/m^2 or > 35 kg/m^2
9. Any clinically significant (in the opinion of the Investigator) hematology or chemistry test results at screening, including any liver function test > 3x the upper limit of normal (subjects with elevated bilirubin due to Gilbert syndrome are eligible to participate)
10. Documented history of anti-insulin antibodies
11. Treatment with glucocorticosteroids, immunosuppressants, or cytostatic agents within 60 days before screening (newly-prescribed or high-dose corticosteroids are prohibited; chronically administered oral, inhaled, topical, or intra-articular corticosteroids at a stable dosage are allowed if no increase in dose is anticipated during the study; See Appendix 3 [Section 17.3] for a list of allowed and prohibited medications)
12. Current use of medication intended to cause weight loss or weight gain
13. Alcohol or substance use disorder within the 2 years before screening
14. Any previous or anticipated treatment with interferons
15. Any history of malignant disease within 5 years before screening, except for adequately treated basal cell carcinoma
16. Severe concomitant physical or psychiatric diseases or conditions
17. A history of a positive test result for HIV, hepatitis B, or hepatitis C; any subject who has a positive test result during the study may continue at the discretion of the Investigator
18. Any history of pancreatitis or pancreatectomy

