#### 8.4.2 Exclusion Criteria

1. Participation in another clinical study or use of any study drug within 30 days before screening
2. Previous use of a biosimilar insulin, either basal or bolus
3. Diabetic ketoacidosis within a year before screening
4. Brittle type 1 diabetes mellitus within the year before screening (e.g., multiple hospitalizations related to diabetes mellitus and/or severe hypoglycemia for which the subject required 3rd party assistance)
5. Any severe, delayed sequela of diabetes mellitus, e.g., worsening end-stage renal disease, advanced coronary artery disease, or myocardial infarction within the year before screening, or autonomic peristaltic problems, e.g., gastroparesis
6. Anticipated change in insulin used during the study (change in dosage is allowed, but change in type or brand of insulin will result in the subject being withdrawn from the study)
7. Inadequately controlled thyroid disease, as reflected by a TSH value or free T4 > the upper limit of normal
8. BMI < 19 kg/m^2 or > 35 kg/m^2
9. Any clinically significant (in the opinion of the Investigator) hematology or chemistry test results at screening, including any liver function test > 3 × the upper limit of normal (subjects with elevated bilirubin due to Gilbert syndrome are eligible to participate)
10. Documented anti-insulin antibodies in the past
11. Treatment with glucocorticosteroids, immunosuppressants, or cytostatic agents within 60 days before screening (newly-prescribed or high-dose corticosteroids are prohibited; chronically administered oral, inhaled, topical, or intra-articular corticosteroids at a stable dosage are allowed if no increase in dose is anticipated during the study; see [Appendix 3](#) [[Section 17.3](#)] for a list of allowed and prohibited medications)
12. Current use of medication intended to cause weight loss or weight gain
13. Alcohol or substance use disorder within the 2 years before screening
14. Any previous or anticipated treatment with interferons
15. Any history of malignant disease within 5 years before screening, except for adequately treated basal cell carcinoma
16. Severe concomitant physical or psychiatric diseases or conditions
17. A history of a positive test result for HIV, hepatitis B, or hepatitis C; any subject who has a positive result during the study may continue at the discretion of the Investigator
18. Any history of pancreatitis or pancreatectomy

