11.3 Important Protocol Deviations

Per PRA processes, protocol deviations data will be entered into the CTMS, in accordance with the Protocol Deviation Guidance Document. The study team and the sponsor will conduct on-going reviews of the deviation data from CTMS, without regard to treatment assignment in accordance with the Blinding Plan. The per protocol analysis sets determined by types of important protocol deviation must be finalized at the data review meeting (or earlier), prior to database lock.

Based on the protocol deviations data entered into CTMS, the important protocol deviations thought to potentially impact the statistical analyses or subject safety will be listed and tabulated using incidence and percentages by deviation type and randomized treatment group in the FAS. Important protocol deviations are defined in the protocol deviation guidance document. The last approved version of protocol deviation guidance will be finalized before the database lock.

1) Immunogenicity-Interfering Important Protocol Deviations (IIIPD)

Important Protocol Deviations are subdivided into those that are thought to interfere with immunogenicity and those that do not. These immunogenicity-interfering important protocol deviations (IIIPD) are listed explicitly in Appendix 4 Immunogenic- and Efficacy-Interfering Important Protocol Deviations and will be used to identify those subjects that are excluded from the Per Protocol Analysis Set 2 (See Section 8.3). This study population will be used in a sensitivity analysis defined in Section 11.6.1.3.

2) Efficacy-Interfering Important Protocol Deviations (EIIPD)

Important Protocol Deviations are also classified into those that are thought to interfere with HbA1c and those that do not. These efficacy-interfering important protocol deviations (EIIPD) are listed explicitly in Appendix 4 and will be used to identify those subjects that are excluded from the Per Protocol Analysis Set 3 (See Section 8.3). This study population will be used in a sensitivity analysis defined in Section 11.7.1.3.

A manual summary of subjects with one or more defective IP pens will be provided and discussed in the clinical study report based on information collected outside of the clinical database. This manual summary will include subject ID, site, investigator name, product quality issue reported, and site / clinical research associate comments.

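### SAP Appendix 4 has no row for an actual breach of exclusion 7 (thyroid value above the upper limit) and grades untested subjects by a two-sided test on later results, so PPS2 and PPS3 can misclassify subjects

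*SAP*

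**What the plan says.** **Criterion.** Protocol 8.4.2, no. 7 excludes "Inadequately controlled thyroid disease, as reflected by a TSH value or free T4 > the upper limit of normal". The synopsis sets the same limit: "Inadequately controlled thyroid disease, defined as a TSH or free T4 value > the upper limit of normal". The synopsis also states "Subjects cannot be enrolled or randomized until all inclusion criteria (including test results) are confirmed". That sentence names only the inclusion criteria, but exclusion 7 also needs a laboratory result. Thyroid tests are scheduled at screening, Week 12 and Week 26 (SAP 11.8.4).

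**Coding.** SAP Appendix 4 has two rows for exclusion 7. Both open with "Enrollment of a subject without obtaining TSH and T4 results before randomization".
- Row 7.1 applies when "both TSH and T4 results are within normal ranges measured by the central laboratory after randomization". It is important, with effect on immunogenicity No and on efficacy No.
- Row 7.2 covers enrollment "without obtaining TSH and T4 results before randomization and TSH and/or T4 results are not available or out of normal ranges after randomization". It is important, with both effects Yes.

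**Use.** SAP 11.3 says that the immunogenicity-interfering deviations "are listed explicitly in Appendix 4 Immunogenic- and Efficacy-Interfering Important Protocol Deviations", and the efficacy-interfering ones are handled in the same way. PPS2 drops subjects with the first kind and PPS3 those with the second. PPS drops anyone with an important deviation (Protocol 12.5.3). Importance is defined in a separate deviation guidance document (SAP 11.3). The ERIPD subgroups are built mainly from important deviations coded to the inclusion or exclusion categories (SAP definitions list, item 11).

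**The concern.** The SAP gives its own reason for the PPS3 analysis in 11.7.1.3: interfering deviations may make the arms look more alike than they are. It gives the same reason for PPS in 11.6.1.3. In an equivalence trial that is the direction that matters. The check works only if the coding picks out the deviations it is meant to find.

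For exclusion 7 the coding misses in two ways. The breach itself has no n. 7 row. The rows that do exist grade subjects against a limit that differs from the protocol's, on results obtained after randomization. The neighbouring rows suggest an omission: n. 4, 5, 6, 8 and 10 each describe the breach, and n. 9 covers both missing and abnormal results. Only n. 7 is confined to missing results.

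**Working it through.** The plan states no figure on this point, so the check is to run each case through the rules as written.

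**Step 1. Classification.**

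| TSH/free T4 before randomization | After randomization | n. 7 row | PPS | PPS2 and PPS3 |
|---|---|---|---|---|
| Above ULN (the breach) | Any | None | Depends on the guidance document | In, unless another row applies |
| None in hand | Both in range | 7.1 | Out | In |
| None in hand | Above ULN | 7.2 | Out | Out |
| None in hand | Only below the lower limit | 7.2 | Out | Out |
| None in hand | Not available | 7.2 | Out | Out |

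The first and fourth lines do not fit the criterion. In the first, exclusion 7 was breached and no n. 7 row applies. In the fourth, the subject is graded as interfering on a value that the criterion does not exclude.

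**Step 2. Does row n. 9 catch the breach?** Row n. 9 (Yes/Yes) covers screening hematology or chemistry results that the investigator considers clinically significant, and enrollment without those tests. There are two readings.
- *Thyroid tests are not chemistry.* The safety-assessment rows of Appendix 4 list thyroid labs separately from chemistry, and SAP 11.8.4 gives them their own group. Then n. 9 catches nothing here.
- *Thyroid tests are part of the panel.* Protocol Table 1, footnote d, places them in routine laboratory testing. Then n. 9 catches a breach only if the investigator considers it significant, whereas exclusion 7 is a fixed limit. In addition, a subject without thyroid tests fits both 7.1 (No/No) and the missing-test part of n. 9 (Yes/Yes), which contradict each other.

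Appendix 4 needs correction on either reading.

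**Step 3. Which result counts?** Row 7.1 requires that "both TSH and T4 results are within normal ranges measured by the central laboratory after randomization (during the treatment period"). Take a screening sample above ULN that is reported after Day 1, with normal values at Weeks 12 and 26.
- If only samples drawn on treatment count, the subject is 7.1 and stays in PPS2 and PPS3.
- If the late report counts as a result after randomization, the subject is 7.2 and leaves both.

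The rows do not settle this. They also do not say which visit decides when Weeks 12 and 26 disagree.

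**Step 4. Illustration of the two-sided test.** Assume 95% reference intervals, independent results, and that any out-of-range value triggers 7.2 (none of this is in the documents). For an untested subject with normal thyroid function and two analytes:
- One visit: any flag 1 − 0.95² = 9.8%; upper-limit flag 1 − 0.975² = 4.9%.
- Two visits: any flag 1 − 0.95⁴ = 18.5%; upper-limit flag 1 − 0.975⁴ = 9.6%.

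The differences, 4.8 and 8.9 percentage points before rounding, are subjects flagged on low values alone. That is about half of all flags in such subjects. If the two visits were fully correlated, the one-visit figures would apply.

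**The case against.** The strongest reply is that these flags grade a deviation's likely effect on the endpoint, not eligibility. Thyroid status during treatment is a plausible basis for that, and the SAP uses the same two-sided convention for its on-study thyroid function abnormality (definitions list, item 24). Exclusion on post-randomization events is not peculiar to these rows either: wrong study drug removes subjects from both sets, and missed doses from PPS3. Deviations are reviewed without regard to treatment assignment. All of this stands, so post-randomization selection alone is not the fault here. It does not explain why the breach has no row, or why the limit in the rows departs from the criterion under which they are filed.

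A reader might infer four stronger things that the documents do not support.
- *All per-protocol sets are affected.* Rows 7.1 and 7.2 are both important, so PPS drops both. Whether PPS keeps a known breach depends on the guidance document, which is not among the documents.
- *True violators certainly stay in.* Row n. 9 may catch some. Other parts of Appendix 4 (the inclusion rows, n. 1–2, n. 12–21 and the Other category) are not in the public text. Rows n. 6 to n. 8 run without a break, so a lost n. 7 row is unlikely.
- *Eligible subjects are dropped.* Subjects under 7.2 had no result in hand at randomization, which is already a deviation. In most such cases screening eligibility is unknown rather than shown.
- *The screening sample is ignored.* That is one of the two readings in Step 3.

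**Conclusion.** The point holds for PPS2 and PPS3. Read as written, Appendix 4 can keep a subject with a known breach of exclusion 7, and it removes untested subjects whose only abnormal value is a low one. It also leaves open which result decides.

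The missing row carries into the ERIPD subgroups used in the adverse-event summaries (SAP Table 6, Analysis 13). The 7.1/7.2 split does not, since both rows are important exclusion-criterion deviations. The primary analysis in the Safety Set and the main HbA1c analysis in the FAS are unaffected.

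The size is unknown. If 1% to 5% of the 550 subjects were randomized without results or above ULN (an assumption), the pool is 5.5 to 27.5, or about 6 to 28. A reader might take this as the number misclassified. It is not: many would get the same grade under a corrected rule, for example a late but normal screening sample followed by normal values. The correction should be made because the defect is clear from the text and cheap to repair, but its reach is limited to supportive analyses.

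**What to change.** In SAP Appendix 4:
1. Add an n. 7 row for screening TSH or free T4 above ULN: important, with both effects Yes, as 7.2 already has.
2. Where a screening sample was reported after randomization, grade the subject on that sample with the protocol's one-sided limit.
3. In 7.1 and 7.2, replace the two-sided range test by above or not above ULN. For subjects with no screening result at all, name the post-randomization result that counts.
4. State that missing thyroid tests are coded under n. 7 and not n. 9.
5. Re-derive the PPS2, PPS3 and ERIPD flags, and the PPS flag for the new row, before database lock, by when SAP 11.3 requires the per-protocol sets to be final.

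Removing every subject without an evaluable screening sample, even with normal values throughout treatment, would reverse a choice that the SAP has made. It is not needed to repair the defect.

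The cost is a wording change and a re-run of the flags on central-laboratory data already held. Some subjects, probably few, would move between supportive sets.
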